Data Analysis Plan for Aims 1 & 2. In this intent-to-treat study, we will collect data on 160 subjects. The biostatistician will monitor the data for distribution normality and transform abnormally distributed variables if needed. Correction for Multiple Comparisons: To minimize spurious findings, we will adjust the 3 primary tests using a false discovery rate at 0.05 (see below). Covariates: Although randomization should protect against group differences, we will covary for any between-group differences that are observed regarding demographic, cognitive, clinical and vocational history, booster sessions, and the number of completed interviews. Missing Data: We will follow the intent-to-treat principle and in longitudinal analyses we will use multiple imputation models to analyze the data in the presence of missing data. Data processing and cleaning will occur during the study, including checking for missing data and inconsistencies. All videos will be stored on the project's secure server. A Data Safety and Monitoring Board will monitor for adverse events (see 15.0 below).

**Hypothesis 1:** IPS+VR trainees will have higher employment rates than IPS Only by T3. **To test H1**, we will use multiple logistic regression and a Wald Chi-square test of the coefficient to its standard error, to compare the adjusted employment proportions in the two conditions (attained a job=1 vs. failed to attain a job or censored with a job=0, between T1 and T3). We calculated power using simulation in R, correcting for small samples and multiple testing with false discovery rate for the 4 primary tests (our power analysis is conservative, relying on Bonferroni corrections for all tests). Accounting for 10% missing, our trial that recruits 80 subjects in each arm has 80% power for a two-sided 0.05/4=.0125 level test when the OR = 3.2, with IPS+VR effectively doubling the

rate from 25% to 53% employment. Based on our earlier study where we found an OR of 8.7, or effectively tripling the employment rate from 25% to 75%, and a power of 0.99 at this magnitude of effect, we feel confident that we will have sufficient power in this study.

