**Hypothesis 2:** IPS+VR trainees will have greater improvement in *job interview skills* than IPS Only by T2. **To test H2**, we will conduct a repeated measures analysis of variance (RM-ANOVA) with pre and post interview scores as the repeated measures and treatment group as the fixed factor. Based on our pilot data, we expect r=.7 between T1 and T2 scores, and an effect size of d=.67 between pre and post interview role-play scores using VR. Assuming a small-to-moderate effect within IPS Only (e.g., d=.25), our best power estimate assumes a medium effect size contrasting IPS Only with IPS+VR (d=.67-.25=.42). This effect size and correlation imply an expected 6.9% reduction in within subject error for the treatment–x-time effect. Thus, 80 subjects at .0125 level will yield 82% power to detect this effect. For the ANOVA model, 160 subjects will be sufficient to detect a reduction of within subject error of 4.7% with 80% power. Assuming a full sample effect size of d=.46 (.67+.25)/2), this reduction in error corresponds to an effect size of d=.62 for the IPS+VR group and d=.30 in the IPS only group (a difference of d=.32).

**Hypothesis 3:** IPS+VR will get jobs sooner than IPS only by T3. **To test H3**, we will use a Cox proportional (or non-proportional) hazards regression model to assess the adjusted hazard rate on time-to-employment for IPS+VR vs. IPS Only, adjusting for potential covariates (e.g., completed training trials). For a power analysis for **H3**, we assume a constant hazard rate for the distribution of time-to-employment in both groups. We also assume that a proportion of 0.20 of the subjects in the IPS Only group will find a job by T3 (that is, a hazard rate of 0.0085 for IPS Only). This analysis is estimated based on limited pilot data and log-rank power tables. Thus, 160 subjects provide 80% power for a 0.0125-level test comparing time-to-employment in the two arms to detect a hazard rate of 2.0 for IPS+VR vs. IPS Only.

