**Hypothesis 4:** IPS+VR trainees will have greater reductions in psychological distress than IPS Only between T1 and T3. **To test H4**, groups will be contrasted on change via RM-ANOVA with time as a repeated measure and group as the main effect. Power analyses for RM-ANOVA focused on contrasts between T1 and T3. A correlation of r=.5 between T1 and T3 was assumed. Power was estimated for a range of relative effect sizes (d=.2 to d=.8; difference between IPS Only and IPS+VR) for RM-ANOVA time-by-treatment interaction effects. Assuming an overall reduction in distress of d=.5 (across both groups), all relative effect sizes were centered on this average (e.g., a relative difference in d=.8, corresponds to d=.9 for IPS+VR and d=.1 for IPS, averaging out to d=.5 overall). For ANOVA change contrasts of IPS only vs. IPS+VR between T1 and T3, 160 subjects will be sufficient to detect d=.50 (d=.75 vs .25) with 80% power for 0.0125-level test. ANCOVA will test for differences in T3 distress while covarying for T1 distress. Baseline differences (e.g., cognition) will be tested as covariates.

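### H1 and H3 have no fixed baseline covariates: H1 adjustment follows whatever arm differences are observed and H3 adjustment is left open, so both models are settled after arm data are seen

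*Combined protocol and SAP*

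**What the plan says.** Section 14.0, under the covariates heading for Aims 1 and 2, concedes that randomization should balance the arms and then states one rule: "we will covary for any between-group differences that are observed regarding demographic, cognitive, clinical and vocational history". The same sentence extends the rule to "booster sessions, and the number of completed interviews", which are not baseline variables. It does not say which variables are compared, by what test, or what counts as a difference.

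The hypotheses then differ:

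- **H1:** "we will use multiple logistic regression and a Wald Chi-square test of the coefficient to its standard error". The comparison is of adjusted proportions, but no adjustment variable is named.
- **H2:** the pre-test interview score is in the model as a repeated measure.
- **H3:** a Cox model "adjusting for potential covariates (e.g., completed training trials"). The single example is a post-randomization quantity.
- **H4:** the ANCOVA always includes T1 distress. The plan adds "Baseline differences (e.g., cognition) will be tested as covariates".

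Randomization (section 4.0, D.4) uses blocks of six with no stratification factor stated, so the design supplies no covariate either. The baseline visits (section 4.0, D.2 and D.3) collect a good deal that might predict employment: work history, the MCCB, symptom scales, role-play interviews, interview self-efficacy and interview anxiety.

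**The concern.** In a randomized comparison a baseline difference between arms is chance. It says nothing about whether the variable predicts getting a job, which is what makes adjustment worthwhile. A rule keyed to imbalance therefore admits irrelevant variables that happen to differ and gives no reason to admit strong predictors that happen to be balanced. Because a difference is not defined, two analysts could apply the rule to the same data and fit different models.

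For H1 the adjusted odds ratio, and for H3 the adjusted hazard ratio, cannot be tied to a stated model before arm data are inspected. These measures also change meaning with the covariates included, so the quantity being estimated is open as well. The protocol describes the trial as confirmatory, so the model should be fixed in advance.

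**Working it through.** **1. Reproduce the plan's H1 power.** The H1 paragraph gives the sample size, attrition and target: "Accounting for 10% missing, our trial that recruits 80 subjects in each arm has 80% power". It sets the level at two-sided .0125 and the effect at OR 3.2, and equates this effect with moving the "rate from 25% to 53% employment".

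- Analysed per arm: 80 × (1 − 0.10) = 72.
- OR 3.2 from 25%: odds = 3.2 × (0.25/0.75) = 1.067, so p2 = 1.067/2.067 = 0.516. The stated 53% corresponds to OR 3.38.
- Pooled two-proportion formula with z = 2.498: mean rate 0.383; null SE = √(2 × 0.383 × 0.617/72) = 0.0810; alternative SE = √((0.25 × 0.75 + 0.516 × 0.484)/72) = 0.0779.
- Power = Φ((0.266 − 2.498 × 0.0810)/0.0779) = Φ(0.82) = 79.3%.
- The Wald log-odds version gives about 77% at OR 3.2 and 81.2% at 53%.

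The stated 80% is therefore reproduced by an unadjusted calculation. It takes no credit for covariates.

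**2. How often would the rule act?** Assume that a difference means p<.05 and that the k variables are independent (the plan states neither). The chance that at least one enters is 1 − 0.95^k: 40% for k = 10, 64% for k = 20 and 79% for k = 30. The expected number entering is 0.05k, or 0.5, 1.0 and 1.5.

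**3. Power with one baseline predictor.** Logistic models were simulated with 72 per arm, marginal rates held at 25% and 51.6%, and two-sided .0125. Ranges cover repeated runs of 4,000 to 6,000 trials. Monte Carlo SE is √(0.8 × 0.2/4,000) = 0.6 points, or 0.5 points with 6,000.

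| Predictor, OR per SD (assumed) | No adjustment | Adjust if p<.05 | Always adjust |
|---|---|---|---|
| 1.2 to 1.4 | 79.1-80.1% | not tabulated | 79.0-80.3% |
| 1.8 | 79.8-80.2% | 80.0-80.6% | 82.0-82.6% |
| 2.7 | 79.8-80.2% | 80.0-80.6% | 85.9-86.7% |

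**4. Several candidates.** With ten independent baseline variables, two or three of them prognostic (4,000 trials):

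| Log-OR per SD (assumed) | No adjustment | Adjust if p<.05 | Always adjust for the prognostic ones |
|---|---|---|---|
| 0.4, 0.4 | 81.2% | 80.0% | 82.9% |
| 0.7, 0.7 | 79.0% | 78.8% | 85.9% |
| 1.0, 0.7, 0.5 | 79.6% | 79.0% | 88.9% |

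The imbalance rule picked up any truly prognostic variable in only 9-14% of trials.

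**5. Type I error for H1.** Under the null (25% in both arms, 8,000 trials, Monte Carlo SE 0.12 points), the p<.05 rule rejected in 0.85-1.19% of trials against a nominal 1.25%. If the analyst could take the most favourable of no adjustment and three thresholds, rejection was 1.3-1.6%.

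**6. Effect on the odds ratio.** With marginal rates fixed at 25% and 51.6%, the odds ratio conditional on the predictor is 3.49 when the predictor has OR 1.8 per SD and about 4.0 at OR 2.7, against 3.2 unadjusted.

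No H3 power was computed for this point. H3 rests on the wording alone.

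**The case against.** The plan does not say that covariates enter only when the arms differ. H1 is described unconditionally as a multiple regression with adjusted proportions, so a fixed set may have been intended. That is fair, but no such set is stated, and observed difference is the only selection rule given.

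A reader might infer that H3 is also triggered by imbalance. Its own sentence does not support that: it is open-ended. The defect there is an unspecified set whose one example is not a baseline variable.

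A reader might extend the point to every primary model. The documents do not support that either. H2 already uses the pre-test score and H4's ANCOVA already fixes T1 distress. The H4 sentence about baseline differences is ambiguous, since it could mean testing variables for relation to the outcome.

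The power gain is not assured. Nothing in the documents shows that work history or cognition predicts employment in this population, and a weak predictor gains nothing. That objection stands, so the gain must be stated as conditional. It also stands that 40% with ten variables does not justify saying that some variable will usually differ.

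**Conclusion.** The point holds for H1 and H3 as a matter of model specification: no baseline covariate is fixed for either, and the rule that is given selects on the wrong property.

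For H1 the imbalance rule leaves power at about 79-81%, the same as ignoring the baseline data. A fixed predictor leaves it at about 79-80% if weak and raises it to 82-83% or 86-87% if moderate or strong. These figures assume a p<.05 trigger, normally distributed baseline variables and the listed strengths, none of which the documents supply.

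A reader might infer that choosing covariates this way inflates the false-positive rate. The check does not support that. A fixed threshold is, if anything, slightly conservative, and even free choice among rules adds only a fraction of a percentage point. The case for change rests on an unfixed model and forgone power. It is worth making because the change is cheap.

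**What to change.** For H1 and H3, drop the imbalance rule and the open-ended wording. Name a short list of variables measured before randomization and expected to predict employment, and include them whether or not the arms differ. Candidates already collected are days worked over the previous five years (Employment History Interview) and the MCCB score. The choice is the team's to justify. Report the unadjusted result as a sensitivity analysis.

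Fix and date the list before anyone choosing it has seen arm-level outcome data. This must cover the statistician who presents preliminary data in the closed DSMB sessions (section 15.0). If that access has already occurred, someone without it should set the list.

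No change is needed to H4's T1 distress covariate or to H2's pre-test score.

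The cost is SAP wording and a few degrees of freedom, with no new data and no change in sample size. The H1 odds ratio becomes conditional (about 3.5-4.0 instead of 3.2 at the same rates, for predictors of OR 1.8-2.7 per SD), so adjusted proportions by arm should be reported with it.

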### F. Participant Timelines

**F. 1. Thresholds Clients.** Individuals receiving mental health services at Thresholds who are enrolled in the effectiveness trial will participate in the study for a period of 9 months. Over the first month, they will complete a series of study measures and if randomized to the intervention group, this participation will include up to 10 hours of virtual reality training. After the first month, the participants randomized to the training group are

welcome to use the training as-needed, which will be monitored using their ID number. Then approximately 6 months after participants complete their post-test visit, they will be invited to complete their 6-month follow-up visit. Approximately 3 months after the 6-month visit, participants will be contacted via phone for a 9-month follow-up interview. Their participation in the study will end at this time.

After 1/3 of the effective trial participants have completed their intervention training (and before the completion of the 6 month follow-up) 20 VR trainees will be recruited to participate in a series of focus groups.

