### Withdrawal of Participants

The above noted cases regarding suicidality and symptom exacerbation are the anticipated situations when the participant will be withdrawn without their consent.

Participants withdrawn from research will:

- not be called to participate in future research visits for the current study;
- have their data included in all analyses unless there is a formal, written request by the participant to have their data removed from analyses (as noted in the consent form).

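### H1 scores anyone lost without a recorded job as a failure, does not say whether the planned imputation covers H1, and counts jobs over a window with no fixed end.

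*Combined protocol and SAP*

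**What the plan says.** **Coding.** Section 14.0, Hypothesis 1, compares employment by logistic regression with a Wald test and codes the outcome as "attained a job=1 vs. failed to attain a job or censored with a job=0, between T1 and T3".

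**Missing data.** The same section invokes intent-to-treat and adds that "in longitudinal analyses we will use multiple imputation models to analyze the data in the presence of missing data". It does not say whether the single binary H1 outcome counts as longitudinal. The power sentence reads "Accounting for 10% missing, our trial that recruits 80 subjects in each arm has 80% power for a two-sided" test at 0.0125 for an odds ratio of 3.2, described as raising the "rate from 25% to 53% employment". It does not say whether the missing are removed or scored 0.

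**Withdrawal.** Under Withdrawal of Participants (section 10.0), withdrawn people will "not be called to participate in future research visits for the current study" but will "have their data included in all analyses unless there is a formal, written request by the participant" to remove them.

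**Timing.** The Specific Aims place H1 to H4 at 6-month follow-up, and Hypothesis 2 ties T1 and T2 to the pre- and post-interview scores. T1 is therefore pre-test and T3 the 6-month follow-up. Section 4.0 F places post-test at about one month and says that about 6 "months after participants complete their post-test visit, they will be invited to complete their 6-month follow-up" visit. Section 4.0 D.4 puts randomisation after the pre-test role-plays. D.5 puts post-test after six training visits in the VR arm. For the control arm, nothing beyond the first month is stated. The scheduling rules after D.8 let Visit 11 stay unscheduled until 6 weeks past due. Staff then pull what the health record holds and participation ends. Visit 10 follows the same process.

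**The concern.** A proportion employed by T3 can be compared between arms only if unknown status is handled in one stated way and both arms are observed for the same time. H1 secures neither.

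Two analysts could follow section 14.0 and run different versions of the first-listed hypothesis: one scoring lost participants 0, the other imputing them. Scoring 0 lowers the observed rate in whichever arm loses more people. A late 6-month visit does the opposite, because it gives more time to find a job.

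The job attainment rate is also the effectiveness measure in H5, where its between-group difference is the denominator of the cost-effectiveness ratio. Any distortion carries over. The Cox model in H3 accommodates differing follow-up but repairs neither H1 nor H5.

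**Working it through.** **Inputs from the plan (section 14.0):** 80 per arm, 10% missing, two-sided 0.0125, 25% in IPS Only, odds ratio 3.2 or 53% in IPS+VR. **Assumptions, not in the documents:** how loss splits between arms, how many lost jobs are still captured, that lost participants find jobs at their arm's rate, constant hazard, and delay. Power is by exact binomial enumeration of the unadjusted Wald test of the log odds ratio.

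**1. The plan's own figure.** Odds at 25% are 1/3. Then 3.2 × 1/3 = 1.067, and 1.067/2.067 = 51.6%. The 53% figure gives an odds ratio of (0.53/0.47)/(1/3) = 3.38. With the missing removed, n = 80 × 0.9 = 72 per arm, and power is 79.7% at 51.6% or 84.2% at 53%. The stated 80% reproduces at odds ratio 3.2.

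**2. Lost participants scored 0 (80 per arm).** Coded rate = p × [1 − loss × (1 − captured)].

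| VR rate | Loss, IPS Only / VR | Captured | Coded rates | OR | Power |
|---|---|---|---|---|---|
| 51.6% | 10% / 10% | none | 22.5% vs 46.5% | 2.99 | 75.5% |
| 51.6% | 10% / 10% | half | 23.75% vs 49.0% | 3.09 | 79.9% |
| 53% | 10% / 10% | none | 22.5% vs 47.7% | 3.14 | 80.3% |
| 51.6% | 5% / 15% | none | 23.75% vs 43.9% | 2.51 | 56.9% |
| 51.6% | 15% / 5% | none | 21.25% vs 49.0% | 3.57 | 88.8% |

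The stated 80% thus fits removal at odds ratio 3.2, and it also fits scoring 0 at 53%.

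**3. No true effect.** With 25% in both arms, rejection is 1.1%. Loss of 15% vs 5% in either direction creates a false difference of 0.25 × (0.95 − 0.85) = 2.5 points, and rejection becomes 1.6% (1.2% if half are captured).

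**4. H5, costs held fixed, none captured, odds ratio 3.2.** The true difference is 51.6 − 25 = 26.6 points. The ratio is multiplied by 0.2661/0.2395 = 1.11 with equal 10% loss, by 0.2661/0.2012 = 1.32 with 5% / 15%, and by 0.2661/0.2778 = 0.96 with 15% / 5%.

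**5. Window.** From entry, the nominal 6-month visit is at 4.3 + 26 = about 30 weeks. If post-test and the 6-month visit each run 6 weeks late, it is at 4.3 + 6 + 26 + 6 = about 42 weeks. Taking 25% as reached at 30 weeks, F(t) = 1 − 0.75^(t/30) gives 22.1% at 26 weeks, 27.8% at 34, 29.2% at 36 and 33.2% at 42. If only VR ran 4 or 6 weeks late with no true effect, the odds ratio would be 1.16 or 1.24 and rejection 1.8% or 2.7%, instead of 1.1%.

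**6. The plan's only time figure.** H3 assumes 20% employed by T3 at hazard 0.0085. That implies −ln(0.80)/0.0085 = 26.25 time units, about 6 months if the unit (not stated) is weeks. Using 26 weeks as the reference in step 5 gives 1 − 0.75^(30/26) = 28.2% at 4 weeks late and 1 − 0.75^(32/26) = 29.8% at 6, slightly more than the 27.8% and 29.2% above.

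**The case against.** Scoring unknowns as failures is an accepted, pre-stated rule that keeps every randomised participant. Follow-up effort is substantial: monthly calls, email, text, letter, contact with the employment specialist and clinician, and finally the health record. With half of the lost jobs captured, power at odds ratio 3.2 is about what removal gives. The larger figures need threefold unequal loss and no capture. They also use 0.0125, the power-calculation level; the planned correction is a false discovery rate at 0.05, and at 0.05 the 56.9% case is 77.7%.

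Most of this stands and limits the size of the point. It does not remove it. The rule sits beside an imputation sentence of unclear scope, and no sensitivity analysis is planned for H1. Calls begin only after post-test (D.7), so someone lost at Visit 10 has mainly the health record, and no section says how a silent record is scored.

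Four stronger readings are tempting and not supported:

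- *A documented job followed by censoring scores 0.* The words allow it, but it contradicts the code of 1 for attaining a job. It is a wording defect.
- *T1 and T3 are unknown.* They can be inferred, as above. What is missing is a fixed end to the window.
- *The stated power is wrong.* Steps 1 and 2 do not show that.
- *The comparison is biased for or against VR.* Only the VR arm must finish six sessions before post-test, but nothing shows that loss or lateness differs by arm.

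Section 4.0 F also says clients "will participate in the study for a period of 9 months", while its parts add to 1 + 6 + 3 = 10 months. Among approximate intervals this is a side issue.

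**Conclusion.** The point holds as an inexpensive improvement that should be made. The H1 code imputes failure to people lost without a recorded job, the scope of the imputation is unstated, and the job-counting window is not fixed from randomisation.

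The documented consequence is modest. Under equal 10% loss with nothing captured, the effect is attenuated from odds ratio 3.2 to 2.99, and power is about 4 points below removal at either effect figure (75.5% vs 79.7%; 80.3% vs 84.2%). Equal lateness adds events and does not create a false difference under no effect. Unequal loss or lateness would bias H1 and the H5 job-rate difference, but the documents give no arm-specific loss or delay, so direction and size remain unknown. Confidence is high on the gaps in the text and low on their practical impact.

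**What to change.** 1. Reword the code: score 1 for any job started after randomisation and by the cut-off, whatever happens later. This also keeps a job already held by an underemployed entrant from counting.
2. Use one cut-off in days from randomisation, the same in both arms, for H1, H3 censoring and the H5 job attainment rate. The sponsor should set it no later than the on-schedule 6-month visit, for example 6 months (about 182 days). That visit comes about 6 months after post-test, and post-test follows randomisation, so participants seen on time are classified from observed data. A cut-off at 1 + 6 months, such as day 210 from randomisation, looks natural but should not be adopted. The first month in section 4.0 F runs from entry, so the visit is nominally about 213 days from entry. If baseline work before randomisation takes more than about 3 days, an on-schedule visit falls before day 210 and creates missing data.
3. Score 0 only when the participant is known to have had no job start through the cut-off. Otherwise multiply impute from arm, baseline variables and monthly-call history, and state that this covers H1. Report missing = 0 as a sensitivity analysis.
4. Record job start dates. The follow-up employment items listed in D.8 and D.10 do not name one, although H3 already needs it.

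The cost is SAP wording, an imputation run and possibly one form field, with no new visits. Two downsides should be accepted openly. Jobs found after the cut-off do not count in H1 (in step 5, 25% at 30 weeks is 22.1% at 26). Participants last observed before the cut-off are imputed or rely on the health record.

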### 3.0 Inclusion and exclusion criteria:

# We will recruit 180 IPS clients at Thresholds diagnosed with a mental disorder with or without psychotic features into the randomized controlled trial. *Inclusion/exclusion criteria are outlined below:*

Inclusion Criteria: 1) Over 18 years old;

2a) all chronic schizophrenia spectrum disorders, including schizophrenia, schizoaffective disorder, delusional disorder, brief psychotic disorder, schizophreniform disorder, other specified schizophrenia spectrum and related disorder, and unspecified schizophrenia spectrum and related disorders;

2b) all bipolar spectrum disorders beyond bipolar type I and II to include cyclothymia, other specified bipolar and related disorder, and unspecified bipolar and related disorders;

2c) all depressive disorders, including disruptive mood dysregulation disorder, major depressive disorder, persistent depressive disorder, other specified depressive disorder, and unspecified depressive disorder;2d) post traumatic stress disorder

3) fluency in English; 4) at least a 4th grade reading level; 5) enrolled in IPS; 6) active IPS enrollee as indicated by at least 1 contacts with his/her Employment Specialist in the past 30 days; 7) currently unemployed or underemployed; 8) Planning to go on interviews within 4 weeks of enrolling in the study; 9) willing to be video recorded; and 10) willing and able to provide informed consent. We will review each participant's medical record to confirm his/her mental health history.

Exclusion Criteria: 1) documented developmental or learning disability; 2) medical condition that may compromise cognition (e.g., Parkinson's Disease, Alzheimer's Disease, Huntington's Chorea, Moderate or Greater TBI); 3) uncorrected vision or hearing problems; 4) active suicidal ideation within the last 30 days with at least some intent to act, with or without a specific plan; this would be reflected in a score of 4 or 5 on the Suicidal Ideation section of the Columbia Suicide Severity Rating Scale (CSSRS); and 5) a past suicide attempt within the past 30 days that did not include preparatory acts or behavior, but was defined by a potentially self-injurious act committed with at least some wish to die as a result of the act.

We will not include any special populations: adults unable to consent; minors; infants; childrens; teenagers (ages 17 and younger); or prisoners.

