Notably, clients will self-report their intention to go on interviews. We will over-select female clients so that they represent ~40% (n=60) of our sample.

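### Section 3.0 recruits 180 while the H1 power statement recruits 160; the H1 power uses 160 before loss and the H2 power uses 160 after loss. Separately, the 80% stated for the H4 change contrast is about 74% at the 160 it cites.

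*Combined protocol and SAP*

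**What the plan says.** Section 3.0 (Inclusion and exclusion criteria) gives the trial's recruitment target: "We will recruit 180 IPS clients at Thresholds". It adds a target for women: "We will over-select female clients so that they represent ~40% (n=60) of our sample".

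Section 14.0 (Data Analysis Plan for Aims 1 & 2) opens with "we will collect data on 160 subjects". The H1 paragraph then describes "our trial that recruits 80 subjects in each arm" and, after an allowance for 10% missing, states 80% power for a two-sided 0.0125 test at an odds ratio of 3.2.

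The later paragraphs mention no loss:
- **H2** (change in interview skills, T1 to T2): "80 subjects at .0125 level will yield 82% power", with a between-group difference of d=0.42 and a correlation of 0.7.
- **H3** (time to employment): 160 subjects.
- **H4** (change in distress, T1 to T3): "160 subjects will be sufficient to detect d=.50", with 80% power at the 0.0125 level and a correlation of 0.5. The sentence refers to ANOVA change contrasts; the same paragraph also plans an ANCOVA of T3 distress on T1 distress.

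Missing data in the longitudinal analyses are to be handled by multiple imputation. No passage links 180 to 160.

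**The concern.** Sections 3.0 and 14.0 both describe the number recruited, and they give different numbers. If 160 is the number before loss, as the H1 paragraph says, it cannot also be the number of complete subjects on which the H2 and H4 powers rest. The stated power of a primary test then depends on which section is read.

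There is a practical consequence too. Section 14.0 has accrual audited against enrolment targets, and section 15.0 asks the DSMB to review recruitment and retention. Neither can be judged against two recruitment numbers and no stated number analysed.

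The H4 figure raises a second question, separate from the first: whether 160 gives the power claimed even when nobody is lost.

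**Working it through.** **Inputs.** Two-sided alpha 0.05/4 = 0.0125 (H1 paragraph). Allocation about 1:1 (section 4.0, D.4, blocks of six). H1: 25% employed in the control arm, odds ratio 3.2. H2: d=0.42, r=0.7. H4: d=0.50, r=0.5. Loss 10% (H1 paragraph only). The H2 and H4 paragraphs give their level as 0.0125 without saying two-sided; I take them as two-sided, as for H1.

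**Candidate numbers analysed.**
- 160 × 0.9 = 144, or 72 per arm
- 160 complete, or 80 per arm
- 180 × 0.9 = 162, or 81 per arm
- 180 complete, or 90 per arm

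**H1, reproducing the plan.** The control odds are 0.25/0.75 = 1/3. At an odds ratio of 3.2 the VR odds are 1.067, a proportion of 1.067/2.067 = 51.6%. (The plan's 53% corresponds to an odds ratio of 3.38; I use the stated 3.2.) A simulated Wald test of the log odds ratio gives:
- 72 per arm: 79.8%, matching the stated 80%
- 80 per arm: 83.9%

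The H1 figure is therefore consistent with 160 recruited and 144 analysed.

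**H2, reproducing the plan.** The group-by-time test in a two-occasion RM-ANOVA is a two-sample t test on change scores. The SD of change, in baseline SD units, is √(2(1−r)) = √0.6 = 0.775. The standardized difference is 0.42/0.775 = 0.542. The noncentrality is 0.542 × √(n/2), with n per arm and 2n−2 degrees of freedom:

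| Analysed | n per arm | Noncentrality | Power |
|---|---|---|---|
| 144 | 72 | 3.25 | 76.4% |
| 160 | 80 | 3.43 | 81.5% |
| 162 | 81 | 3.45 | 82.1% |

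The stated 82% needs 80 complete subjects in each arm. Read as 80 in total, the sentence would give only about 45%.

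From the same 80 per arm, then, H1 takes off 10% and H2 does not.

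**H4, checking the plan.** The SD of change is √(2(1−0.5)) = 1, so the standardized difference is 0.50:

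| Analysed | n per arm | Noncentrality | Power, change contrast |
|---|---|---|---|
| 144 | 72 | 3.00 | 68.1% |
| 160 | 80 | 3.16 | 73.7% |
| 162 | 81 | 3.18 | 74.3% |
| 180 | 90 | 3.35 | 79.6% |

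The stated 80% does not reproduce at 160. The difference detectable with 80% power at 160 is about (2.498 + 0.842) × √(2/80) = 0.53, by the normal approximation.

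**H4 by the planned ANCOVA.** The residual SD is √(1−r²) = √0.75 = 0.866, so the standardized difference is 0.50/0.866 = 0.577. With one further degree of freedom spent on the covariate, power is 86.8% at 160 and 82.3% at 144.

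**Female target.** 60/160 = 37.5%; 60/180 = 33.3%. Forty per cent would be 64 of 160 or 72 of 180.

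**The case against.** **180 and 160 can be reconciled.** 180 less 10% is 162, and the statement that data will be collected on 160 fits that reading. This stands: the two numbers alone are not in conflict. The conflict comes from the H1 wording, which calls 80 per arm the recruited number and allows for the missing 10% there. The reproduction of 80% at 72 per arm shows that the calculation fits those words.

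**The H2 power is not shown to be wrong.** A reader might infer that 82% is an error. The documents do not support that. With 180 recruited and 162 analysed it is correct. The fall to 76% needs 160 to be the recruited number and the 10% of H1, which is measured at the 6-month follow-up, to carry over to T2, the post-test after about a month. No T2 loss rate is given.

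**Multiple imputation could keep all randomized subjects in the analysis.** True, so 160 randomized and 160 analysed is not in itself a contradiction. The 144 figures assume that imputation does not restore the information lost with a missing outcome. The H1 power statement itself makes an allowance for missing data.

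**H4 is not shown to be underpowered.** A reader might infer from 74% that the H4 analysis is too weak, or that the shortfall comes from ignoring loss. Neither follows. The shortfall is there at the full 160, so loss only adds to it; and the ANCOVA in the same paragraph exceeds 80% even at 144. What remains is that the plan attaches its 80% to the change contrast, which does not reach it. A one-sided 0.0125 test would give about 81% at 160, but H1 is explicitly two-sided, and the H2 figure fits a two-sided test (82%) and not a one-sided one (88%).

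**The female target is approximate.** It would be too strong to say that 60 implies a sample of 150: the tilde makes 37.5% of 160 tolerable. Only 33% of 180 fits poorly.

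**Conclusion.** The plan states two recruitment numbers, 180 and 160, and uses 160 as the number before loss for H1 and the number after loss for H2. The effect on H2 is conditional: 82% stands with 180 recruited and 162 analysed, and becomes about 76% with 160 recruited and 144 analysed.

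The H4 discrepancy is a separate error of calculation. At two-sided 0.0125 the change contrast has about 74% power at 160 or 162 and 68% at 144, against 80% stated.

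These figures assume equal SDs, equal arms, the same loss in both arms, and loss treated as lost information. The stated H1 power is sound for 160 recruited. H3 also uses 160 without loss, but its power turns on the number of events; that is a different question and is not part of this point. Nothing here shows that the trial is too small; the powers and the numbers behind them need to agree.

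**What to change.** 1. State one number randomized and one expected number analysed, and use both in section 3.0 and throughout the H1 to H4 paragraphs of section 14.0.
2. Say whether the 10% loss applies to H2, H3 and H4, with a separate rate for T2 if a different one is expected.
3. Restate the powers at the number analysed. With 180 recruited and 162 analysed: H2 82%, H4 change contrast 74%. With 160 recruited and 144 analysed: H2 76%, H4 change contrast 68%. Alternatively, name the ANCOVA as the H4 test and attach the power to it (about 87% at 160, 82% at 144).
4. State that the tests are two-sided in each power sentence, and in H2 say that the 80 subjects are per arm.
5. Align the female target with the chosen number: 40% is 72 of 180 or 64 of 160.

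The cost is wording in the protocol and analysis plan, and some stated powers become less favourable. No extra recruitment is proposed, and no endpoint changes. The H4 test changes only if the ANCOVA is chosen in step 3.
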